## 7. Statistical considerations

### 7.1. Sample size consideration

This prospective non-interventional study is designed to evaluate and compare the performance of 6 imaging-guided techniques with wire-guided localization (WGL). It is hypothesized that the imaging-guided methods perform better or equal to WGL in terms of the likelihood of the intended lesion removal, as well as the likelihood of a negative margin. Each localization device/method will be compared to the wire-guided localization considered standard using propensity scoring. The first co-primary endpoint is the intended lesion removal. The failure rate of WGL in the literature is 0.6%, giving an identification rate of 99.4% [11]. A difference of 1.1% between techniques is considered to be clinically significant. Given an allocation rate of 2:1 for WGL : experimental group, sample sizes of 1854 in the WGL group and 927 in each experimental group are sufficient to restrict the upper boundary of the respective confidence interval for the differences in identification rates of WGL versus experimental device to 1.1% with a power of 80%. The other co-primary endpoint is the positive margin rate. The positive margin rate of WGL in the literature is 15%, yielding a negative margin rate of 85%, respectively [21]. A clinically significant difference between techniques was considered to be less than 5%. Assuming that each experimental method also has a negative margin rate of 85%, the upper limit of the confidence interval for the difference in negative margin rates is limited to 5% with a power of 80.04%. Each commercially available device will be analyzed in a separate cohort. To adjust for multiplicity and to keep an overall type 1 error of 5%, each of the 12 comparisons are planned with an alpha of 0.417%.

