### 7.2. Planned statistical analyses

This prospective cohort study has two independent primary endpoints A and B which will be tested 6 times each to compare each of the imaging-guided techniques separately with wire-guided localization as the gold standard. To control the family-wise error rate at 5% for the 12 tests, a Holm-Bonferroni procedure will be applied.

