### **Endpoint B**

Rate of negative resection margin rates (defined as lesion removal with no invasive or non-invasive carcinoma on ink) at first surgery, to be compared between imaging-guided techniques and WGL.

Hypotheses:

H20:  $P2_{\text{exp}_i} - P2_{\text{WGL}} \leq -0.05$  versus

H21:  $P2_{\text{exp}_i} - P2_{\text{WGL}} > -0.05$ ,

with  $P2_{\text{exp}_i}$ ,  $P2_{\text{WGL}}$  being the negative resection margin rates in the  $i$ th experimental group and in WGL group.

To balance the baseline variables between treatment groups, inverse-probability-of-treatment-weighting (IPTW) is applied to each pairwise comparison. Variables used for balancing include those variables that are associated with the outcome. The IPT weights will be considered for all primary endpoint comparisons.

Analysis of the primary endpoints:

The difference of the rates between the groups (WGL – experimental group  $i$ ) will be calculated and compared to the respective margin. The null hypothesis is rejected, if the lower bound of a defined confidence interval increases the margin.

To define the width of each confidence interval, the Holm-Bonferroni method will be applied:

1. Step: t-tests between each experimental method and WGL will be applied.
2. Step: The hypotheses are ordered by their nominal p-values. Only hypotheses indicating that the effectiveness of imaging-guided technique exceeds WGL are considered here. If none of the hypotheses shows this trend, the hypotheses are ordered by the lower bound of the 95% confidence interval of the estimated beta, starting with the highest number.
3. Step: For the first hypothesis in this order, a  $(100\% - \frac{5\%}{12})$ -confidence interval will be calculated. If the lower bound of this confidence interval increases the respective margin, the null hypothesis is rejected, and the next step will be applied. If the lower bound of this confidence interval does not increase the respective margin, the null hypothesis is accepted, and the procedure ends here.

4. Step: For the next hypothesis in this order, a  $(100\% - \frac{5\%}{11})$ -confidence interval will be calculated, and decisions are made as in the previous step. In each following step, the confidence interval gets incrementally larger, by dividing 5% through the number of untested hypotheses.

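### The stated power needs the 0.417% alpha to be one-sided, but section 7.2 never says its (100% − 5%/12) interval is one-sided; read conventionally, first-step power is about 73% (endpoint B) and 75% (endpoint A)

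*Protocol*

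**What the plan says.** Protocol section 7.1 fixes the design: "sample sizes of 1854 in the WGL group and 927 in each experimental group are sufficient". For endpoint A (intended lesion removal), "The failure rate of WGL in the literature is 0.6%, giving an identification rate of 99.4" per cent, the margin is 1.1 percentage points and the stated power is 80%. For endpoint B (negative margins), both groups are assumed to have a rate of 85%, the margin is 5 points, and "the upper limit of the confidence interval for the difference in negative margin rates is limited to 5% with a power of 80.04" per cent. On multiplicity, "each of the 12 comparisons are planned with an alpha of 0.417" per cent.

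Section 7.2 states one-sided non-inferiority hypotheses for both endpoints and adds "To control the family-wise error rate at 5% for the 12 tests, a Holm-Bonferroni procedure will be applied". It then says "To define the width of each confidence interval, the Holm-Bonferroni method will be applied". The first ordered hypothesis is judged on the lower bound of a (100% − 5%/12) confidence interval, the next on a (100% − 5%/11) interval, and so on. The procedure ends at the first hypothesis that is not rejected. Neither section says whether these intervals are one-sided or two-sided.

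**The concern.** A 99.583% confidence level can mean two decision rules. As a one-sided bound, it puts the whole 0.417% in the tested tail. As an ordinary two-sided interval, it puts half of that, 0.208%, in the tested tail. The wording of 7.2 leans towards the second: it speaks of the interval's width, which a one-sided bound does not have in any finite sense, and it names no side.

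The choice moves the rejection threshold for all 12 primary tests. Because the procedure stops at the first failure, a leading hypothesis whose estimate lies between 2.638 and 2.865 standard errors above the margin is rejected under one reading. Under the other it ends the procedure with no technique declared non-inferior. Two analysts following 7.2 in good faith could therefore report opposite conclusions from the same data.

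**Working it through.** **Inputs (Protocol 7.1 and 7.2).** n(WGL) = 1854 and n(exp) = 927. Endpoint B: 85% in both groups, margin 0.05. Endpoint A: 99.4% under WGL, margin 0.011. Per-comparison alpha: 5%/12 = 0.417%.

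**Assumption.** For endpoint A the experimental rate is not given; 99.4% is taken here, in line with the hypothesis that "the imaging-guided methods perform better or equal to WGL in terms of the likelihood of the intended lesion removal".

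**Formula.** Non-inferiority for two proportions, unpooled normal (Wald) approximation, difference taken as experimental − WGL:

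- SE = √[p(1 − p)(1/1854 + 1/927)]
- power = Φ(margin/SE − z)

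**Standard errors.**

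- B: √[0.85 × 0.15 × (1/1854 + 1/927)] = 0.014364; 0.05/0.014364 = 3.481
- A: √[0.994 × 0.006 × (1/1854 + 1/927)] = 0.0031065; 0.011/0.0031065 = 3.541

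**Step 1: reproduce the plan's figures with one-sided 0.417% (z = 2.638).**

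- B: Φ(3.481 − 2.638) = 80.04%, an exact match. Solving the same formula for 80% power gives 1853 WGL patients against the 1854 stated.
- A: Φ(3.541 − 2.638) = 81.7%, against a stated 80%.

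The match for B shows how the study was sized. The figure for A is close but not exact.

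**Step 2: lower limit of a two-sided (100% − 5%/12) interval.** The tail is 0.05/24 = 0.208%, z = 2.865.

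- B: Φ(3.481 − 2.865) = 73.1%
- A: Φ(3.541 − 2.865) = 75.0%

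| Endpoint | Stated | One-sided 0.417% | Two-sided interval (0.208% in the tail) |
|---|---|---|---|
| A | 80% | 81.7% | 75.0% |
| B | 80.04% | 80.04% | 73.1% |

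**Step 3: what this does to the threshold for B.** Rejection at the first step needs an observed difference above −0.05 + z × SE:

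- one-sided: −0.05 + 2.638 × 0.014364 = −1.21 percentage points
- two-sided: −0.05 + 2.865 × 0.014364 = −0.88 percentage points

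An observed deficit of 1 point would pass under one reading and fail under the other.

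**Step 4: sensitivity to the interval method.** Score (Farrington-Manning), pooled, continuity-corrected and Newcombe versions were also computed. At 0.208% none reaches 80% for either endpoint: B ranges from 68.3% to 73.3% and A from 31.6% to 75.6%. Endpoint A depends strongly on the method: score and Newcombe give only about 44–45% even at one-sided 0.417%.

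**Step 5: the whole Holm procedure.** The ordered procedure was simulated with two-sided intervals, a shared WGL group, endpoints taken as independent and a normal approximation. Per-comparison power was:

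| Techniques truly equal to WGL (others at the margin) | A | B |
|---|---|---|
| all six | about 88% | about 87% |
| three of six | about 79% | about 77% |
| one of six | about 76% | about 74% |

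None of these figures allows for the loss of effective sample size from weighting.

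**The case against.** The strongest reply is that the protocol never says two-sided. The hypotheses are one-sided and only one limit is ever used. The planning alpha, the family-wise 5% over 12 tests and the (100% − 5%/12) level all agree if the interval is a one-sided bound, and the exact match at 80.04% suggests that this is what the authors had in mind. This stands: a reader might infer that 7.2 definitely tests at 0.208%, and the text does not establish that. It does not make the wording safe, because non-inferiority is commonly decided on one limit of a two-sided interval and 7.2 describes the interval by its width. The 95% interval named in Step 2 adds little, since it serves only as a fallback for ordering the hypotheses.

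A second reply is that 73% and 75% are not the power of the trial as analysed. This also stands. A reader might infer that the chance of missing a truly equal technique on endpoint B rises from 20% to 27% throughout, but that holds only at the first, strictest Holm step. Later steps relax: with six hypotheses left, a two-sided interval has 5%/6/2 = 0.417% in the tail, which is the planning alpha. Under 7.1's own assumption for B that every technique equals WGL, the full procedure exceeds 80%. The first-step figure is still the like-for-like comparison, because 7.1 sizes every comparison at 5%/12.

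Third, the two-sided reading is conservative: it makes no false claim of non-inferiority more likely. That is correct. The cost is in power and in an ambiguous decision rule, not in type I error.

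**Conclusion.** The point holds as a mismatch between the stated planning power and the decision rule under the conventional reading of 7.2. It is not proof that the protocol uses two different alphas. For endpoint B, 80.04% requires one-sided 0.417%; the lower limit of a two-sided interval gives 73.1% at the first Holm step, a loss of about 7 points. For endpoint A the corresponding figures are 81.7% and 75.0%, against a stated 80%; these rest on an assumed equal rate of 99.4% and a Wald interval, and are less secure than those for B. The one-sided family-wise error is 5% under one reading and 2.5% under the other. This is more than missing detail, because the protocol itself fixes both the power and the confidence level, and the choice determines whether a borderline first hypothesis opens or closes the whole testing sequence. It should be settled before any comparative data are seen.

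**What to change.** Preferred, because it matches the sample size calculation: in 7.2, define each bound as a one-sided (100% − 5%/k) lower confidence bound, that is, the lower limit of a two-sided (100% − 10%/k) interval, for k = 12, 11, and so on. In 7.1, say that the 5% family-wise error and the 0.417% per comparison are one-sided.

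Alternative, if the two-sided interval is intended: call it two-sided in 7.2 and restate the power in 7.1 as about 73% for B and about 75% for A (Wald interval, equal rates assumed), labelled as power per comparison at the first Holm step.

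The cost is a sentence in each section, or a less favourable planning figure. Neither route changes the sample size.

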### 7.2. Planned statistical analyses

This prospective cohort study has two independent primary endpoints A and B which will be tested 6 times each to compare each of the imaging-guided techniques separately with wire-guided localization as the gold standard. To control the family-wise error rate at 5% for the 12 tests, a Holm-Bonferroni procedure will be applied.

#### **Endpoint A**

Rate of intended target lesion and/or marker removal, independent of margin status on final histopathology, to be compared between imaging-guided techniques and WGL.

Hypotheses:

H10:  $P1_{\text{exp}_i} - P1_{\text{WGL}} \leq -0.011$  versus

H11:  $P1_{\text{exp}_i} - P1_{\text{WGL}} > -0.011$ ,

with  $P1_{\text{exp}_i}$ ,  $P1_{\text{WGL}}$  being the intended lesion rates in the  $i$ th experimental group and in WGL group.

### **Endpoint B**

Rate of negative resection margin rates (defined as lesion removal with no invasive or non-invasive carcinoma on ink) at first surgery, to be compared between imaging-guided techniques and WGL.

Hypotheses:

H20:  $P2_{\text{exp}_i} - P2_{\text{WGL}} \leq -0.05$  versus

H21:  $P2_{\text{exp}_i} - P2_{\text{WGL}} > -0.05$ ,

with  $P2_{\text{exp}_i}$ ,  $P2_{\text{WGL}}$  being the negative resection margin rates in the  $i$ th experimental group and in WGL group.

To balance the baseline variables between treatment groups, inverse-probability-of-treatment-weighting (IPTW) is applied to each pairwise comparison. Variables used for balancing include those variables that are associated with the outcome. The IPT weights will be considered for all primary endpoint comparisons.

Analysis of the primary endpoints:

The difference of the rates between the groups (WGL – experimental group  $i$ ) will be calculated and compared to the respective margin. The null hypothesis is rejected, if the lower bound of a defined confidence interval increases the margin.

To define the width of each confidence interval, the Holm-Bonferroni method will be applied:

1. Step: t-tests between each experimental method and WGL will be applied.
2. Step: The hypotheses are ordered by their nominal p-values. Only hypotheses indicating that the effectiveness of imaging-guided technique exceeds WGL are considered here. If none of the hypotheses shows this trend, the hypotheses are ordered by the lower bound of the 95% confidence interval of the estimated beta, starting with the highest number.
3. Step: For the first hypothesis in this order, a  $(100\% - \frac{5\%}{12})$ -confidence interval will be calculated. If the lower bound of this confidence interval increases the respective margin, the null hypothesis is rejected, and the next step will be applied. If the lower bound of this confidence interval does not increase the respective margin, the null hypothesis is accepted, and the procedure ends here.

4. Step: For the next hypothesis in this order, a  $(100\% - \frac{5\%}{11})$ -confidence interval will be calculated, and decisions are made as in the previous step. In each following step, the confidence interval gets incrementally larger, by dividing 5% through the number of untested hypotheses.

Results of secondary outcomes analyses will be interpreted as exploratory. Descriptive statistics of all baseline variables will be calculated by treatment and also after pooling the image-based methods.

Further, a pooled analysis of the MELODY data with data from iBRA-NET audits is planned.

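### The primary analysis subtracts in one direction (WGL minus experimental) but rejects on the bound that belongs to the other, contradicting the stated hypotheses and Section 7.1

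*Protocol*

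**What the plan says.** Three places in the Protocol give a direction for the primary comparison.

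- **Hypotheses (Section 7.2, Endpoints A and B).** The alternatives are "P1_{\text{exp}_i} - P1_{\text{WGL}} > -0.011" and "P2_{\text{exp}_i} - P2_{\text{WGL}} > -0.05". Higher rates are better on both endpoints, so these are non-inferiority claims for the new technique on experimental minus WGL.
- **Sample size (Section 7.1).** For Endpoint A the group sizes are chosen to "restrict the upper boundary of the respective confidence interval for the differences in identification rates of WGL versus experimental device to 1.1" percent. Endpoint B is likewise planned on an upper limit, of 5%.
- **Analysis of the primary endpoints (Section 7.2, under Endpoint B).** "The difference of the rates between the groups (WGL – experimental group" *i*) is what is calculated and compared with the margin. The decision is: "The null hypothesis is rejected, if the lower bound of a defined confidence interval increases the margin". Step 3 repeats it: "If the lower bound of this confidence interval increases the respective margin, the null hypothesis is rejected, and the next step will be applied". Step 4 takes its decisions in the same way as Step 3.

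I read the verb in the rejection sentence as meaning that the bound exceeds the margin. The sign of the margin is not repeated there.

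**The concern.** There are two equivalent ways to write the intended test: the lower bound of (experimental - WGL) lies above -margin, or the upper bound of (WGL - experimental) lies below +margin. The hypotheses use the first and Section 7.1 the second. The analysis paragraph takes the subtraction from one and the bound from the other.

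A lower bound of (WGL - experimental) above -0.05 shows that WGL is not materially worse than the new technique, which is the converse claim. A lower bound above +0.05 shows that the new technique is worse by more than the margin. Neither is the stated alternative.

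This rule governs all 12 confirmatory tests. An analyst cannot follow both the hypotheses and the rule, and a sign chosen after the data are seen is no longer prespecified.

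**Working it through.** **Inputs.** From Section 7.1: 1854 WGL and 927 per experimental group; WGL rates 99.4% (A) and 85% (B); per-comparison alpha 0.417% = 5%/12. Margins 0.011 and 0.05 come from Section 7.2. The Protocol does not state whether alpha is one- or two-sided.

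**Reproducing the plan's figure.** Normal approximation with unpooled variance, SE = sqrt[pW(1-pW)/1854 + pE(1-pE)/927], z(1-0.00417) = 2.638.

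- B, 85% vs 85%: SE = 0.01436; power = Φ(0.05/0.01436 - 2.638) = Φ(0.843) = 80.04%, as stated.
- A, 99.4% vs 99.4%: SE = 0.00311; power = Φ(0.011/0.00311 - 2.638) = Φ(0.90) = 81.7%, consistent with the stated 80%.
- Total: 1854 + 6 × 927 = 7416, as stated.
- With alpha halved (two-sided, z = 2.865), B gives 73.1%, so the plan was calculated one-sided.

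This power belongs to the coherent rule, on which the hypotheses and Section 7.1 agree.

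**Pass probability for one comparison.** Let d = pW - pE and m be the absolute margin.

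- Literal rule, negative margin: lower bound of (WGL - exp) > -m; probability Φ((d + m)/SE - 2.638).
- Literal rule, positive margin: lower bound of (WGL - exp) > +m; probability Φ((d - m)/SE - 2.638).
- Coherent rule: lower bound of (exp - WGL) > -m; probability Φ((m - d)/SE - 2.638).

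| Endpoint, true experimental rate | Literal, negative margin | Literal, positive margin | Coherent rule |
|---|---|---|---|
| B, 75% | 100% | 65.5% | 0% |
| B, 80% (null boundary) | 99.99% | 0.42% | 0.42% |
| B, 85% | 80.0% | 0% | 80.0% |
| B, 86% | 58% | 0% | 95% |
| B, 88% | 12% | 0% | 99.95% |
| B, 90% | 0.4% | 0% | 100% |
| A, 97% | 99.95% | 33% | 0% |
| A, 98.3% (null boundary) | 98% | 0.42% | 0.42% |
| A, 99.4% | 81.7% | 0% | 81.7% |
| A, 99.9% | 60% | 0% | 100% |

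Example for B at 80%, negative margin: SE = 0.01554; (0.05 + 0.05)/0.01554 - 2.638 = 3.80; Φ = 99.99%.

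**One data set.** Observed 85% vs 75%: SE = 0.01646, and the interval for WGL - experimental is 0.10 ± 2.638 × 0.01646 = 0.057 to 0.143. The lower bound exceeds both -0.05 and +0.05, so the literal rule passes a technique that is 10 points worse. Observed 85% vs 95% gives -0.129 to -0.071, and the better technique fails against either margin.

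**Why the power statement hides it.** At equal true rates d = 0, and the negative-margin and coherent formulas coincide, so the literal rule also returns the planned 80%.

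**Effect of Step 2.** Step 2 considers only hypotheses that favour the new technique, with a fallback ordering if none does. A technique at 80% on B shows a favourable estimate with probability Φ(-0.05/0.01554) = Φ(-3.22), about 0.06%. The harm then moves to the better techniques:

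- With a positive margin, a favourable estimate means WGL - experimental is below zero, so its lower bound cannot exceed +m and no such hypothesis can be rejected.
- With the negative margin on B, a favourable estimate is rejected only while the observed gain is below about 0.05 - 2.638 × 0.0140 = 0.013. Larger gains fail, and the procedure stops at the first failure.

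**The case against.** The strongest reply is that this is one transposed subtraction with an obvious intent. The hypotheses, Section 7.1, Step 2 (which favours techniques exceeding WGL) and Step 3 (lower bound) all fit together on experimental minus WGL. Only the parenthesis defining the difference conflicts. That is right, and it makes the fix small. It does not remove the contradiction: the parenthesis defines the very quantity to which the bound is applied.

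A reader might infer that the procedure as a whole will declare clearly inferior techniques non-inferior nearly always. The Protocol does not support that. The 99.99% and 98% figures are for isolated tests. Under Step 2 an inferior technique is normally set aside when any other comparison looks favourable, and if a clearly better one is tested first it fails and ends the sequence. Inferior techniques reach testing mainly through the fallback.

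A reader might also infer that every better technique fails. With negative margins that is too strong: on B, 86% still passes 58% of the time and 87% passes 32%; on A, where the largest possible gain is 0.6 points, 99.7% passes 70% and 99.9% passes 60%.

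Sidedness moves some values. With a two-sided interval, 65.5% becomes 57% and 12% becomes 8%, while 99.99% becomes 99.98%. The direction is unchanged.

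**Conclusion.** The contradiction is real: as printed, the primary rule tests the wrong direction, and neither sign of the margin rescues it. For one comparison with negative margins, the pass rate at the null boundary is 99.99% (B) and 98% (A) where 0.42% is intended, and on B it falls as the technique improves. With positive margins, an equal technique essentially never passes.

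These sizes assume the planned group sizes and WGL rates, one-sided 0.05/12, a normal approximation (rough for Endpoint A, where failures are few), no weighting and no Step 2 ordering. Inverse-probability weighting would change the variance but not the direction. It is most likely a drafting slip, since the rest of the section shows the intended test, but it sits in the confirmatory rule and should be corrected before the primary analysis.

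**What to change.** In the paragraph on analysis of the primary endpoints, define the difference as experimental group *i* minus WGL, and state that H0 is rejected if the lower confidence bound exceeds -0.011 (Endpoint A) or -0.05 (Endpoint B). As to direction, Steps 3 and 4 then stand as written. Section 7.1 needs no sign change, because an upper bound for WGL minus experimental below +0.011 or +0.05 is the same condition.

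The cost is one phrase and the two signed margins in a protocol amendment. Data collection and the sample size do not change. Power at the planned rates stays at 80.0% (B) and 81.7% (A), and the single-test pass rate at the null boundary is 0.42%.

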### 3. Rationale

In the last decades, the proportion of breast cancer (BC) patients receiving breast-conserving surgery has increased steadily, reaching 70-80% in developed countries [1-3]. Since positive resection margins are strongly associated with local recurrence risk, the goal of breast surgery is the complete tumor removal and most national and international guidelines recommend re-operation, either in form of re-excision or mastectomy, until clear margins have been reached [4]. Re-operation rates vary widely, with population-based studies reporting a range of 15-35%, and the necessity for a second surgery can lead to increased patient anxiety, a delay in start of adjuvant treatment, worse cosmetic outcome and increased complication rates and costs [1,5-9]. Therefore, re-operation rate has been included as a quality indicator in several countries [10].

Several imaging-guided techniques have been developed to guide removal of non-palpable breast lesions, the oldest one being preoperative wire placement under ultrasound or mammographic guidance, usually followed by radiography or ultrasound of removed tissue [11]. Newer techniques, such as intraoperative ultrasound (IOUS), radioguided occult lesion localization (ROLL), radioactive seed localization (RSL), radar reflector-localization (RRL), magnetic localization, and radiofrequency identification (RFID) tags have been introduced as an alternative to wire-guided localization (WGL) [12,13].

To date, comparative data on the rates of successful lesion removal, negative margins and re-operations in patients undergoing different localization techniques are limited. In case of RSL and ROLL, several randomized controlled trials (RCTs) have been conducted, usually comparing these methods to WGL [11]. Regarding IOUS, results from three RCTs with WGL as control arm are available [14-16]. For the other markers that require a special probe to guide intraoperative detection, i.e., magnetic markers, radar reflectors and RFIDs, only data from prospective and retrospective cohort studies are available, which makes a direct comparison between different techniques challenging [17-20]. Further, since some of these studies were funded by the manufacturer of the marker examined, a potential bias cannot be excluded. In the vast majority of the available studies, the patient's perspective with regard to discomfort and pain level has not been evaluated.

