#### **4.4. Registration and therapy**

All patients with invasive or in situ breast cancer scheduled for a breast-conserving surgery and requiring imaging-guided localization should be informed about the possible participation in the MELODY study. The inclusion and exclusion criteria are verified by the investigator and written informed consent is obtained from the patient.

Surgical treatment, pathological assessment and postoperative locoregional and systemic therapy should be conducted according to institutional and national standards. Since the MELODY study is a non-interventional trial, the Study Sites do not deviate from their own institutional protocol at any timepoint.

Diagnostician/radiologist's and Surgeon's satisfaction with the marking and localization technique used are assessed using a short questionnaire.

Patient-reported outcomes are reported using a short questionnaire (to be completed between localization/surgery and postoperative visit).

Patients will be followed for 30 days postoperatively for perioperative complications. No long-term surveillance is required.

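### Section 7.1 states power for independent, unweighted patients with almost no reserve, while section 7.2 plans a weighted comparison of patients nested in sites

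*Protocol*

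**What the plan says.** Protocol section 7.1 sizes each comparison at 1854 wire-guided (WGL) and 927 experimental patients. For endpoint A, with a WGL success rate of 99.4%, the interval for the difference is to be held, "versus experimental device to 1.1% with a power of 80" (per cent). For endpoint B, with 85% assumed in both groups, "the upper limit of the confidence interval for the difference in negative margin rates is limited to 5% with a power of 80.04" (per cent). On the significance level, "each of the 12 comparisons are planned with an alpha of 0.417" (per cent). Section 4.6 sets accrual at 7416.

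Section 7.2 (text under Endpoint B) applies IPTW to each pairwise comparison and says that the weights enter all primary comparisons. The stepwise procedure begins with "t-tests between each experimental method and WGL will be applied". Step 2 uses the resulting p-values to order the hypotheses. The decision comes in Steps 3 and 4: "If the lower bound of this confidence interval increases the respective margin, the null hypothesis is rejected". How the variance of those intervals is obtained is not stated.

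On sites, section 4.4 says that "the Study Sites do not deviate from their own institutional protocol at any timepoint", section 4.5 qualifies sites method by method, and section 4.2 lists site experience by technique as a secondary outcome. Section 3 notes: "Re-operation rates vary widely, with population-based studies reporting a range of 15-35" (per cent). Site appears neither in the sample size nor in the primary analysis.

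**The concern.** The power statement and the analysis describe two different situations. Weighting usually reduces the effective sample size. Patients of one site share surgeons, radiologists and pathology practice, so their outcomes are likely to be correlated. If technique also differs mainly between sites, that correlation inflates the variance of the comparison. A sample size with no reserve then has less power than stated, and a failure to show non-inferiority could reflect too little information and not a worse technique.

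The second part concerns the intervals. The only test that the protocol names is a t-test. If its variance were carried into the intervals of Steps 3 and 4, and technique varied mainly between sites, the intervals would be too narrow. In a non-inferiority comparison, that makes the claim easier to reach.

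**Working it through.** **Inputs from the protocol.** Rates of 85% (B) and 99.4% (A), margins of 5 and 1.1 percentage points, groups of 1854 and 927, level 5%/12 = 0.417% per comparison (section 7.1); accrual 7416 (section 4.6). For A, the experimental rate is taken as equal to the WGL rate, which section 7.1 does not state explicitly.

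**1. Reproducing the stated power.** Formula: power = Φ(margin/SE − z), with SE = √[p(1−p)(1/1854 + 1/927)] and z = 2.638 for a one-sided 0.417%.

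- B: SE = √(0.85 × 0.15 × 0.001618) = 0.01436; 0.05/0.01436 = 3.481; Φ(3.481 − 2.638) = 80.0%. With the level rounded to 0.00417 the result is 80.04%, the stated figure.
- A: SE = √(0.994 × 0.006 × 0.001618) = 0.003107; 0.011/0.003107 = 3.541; Φ(3.541 − 2.638) = 81.7%, against a stated 80%.

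The match for B shows that independent, unweighted patients with complete outcomes were assumed. The level must be one-sided: with 0.208% per side, B gives 73.1%.

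**2. Is there a reserve elsewhere?** 1854 + 6 × 927 = 7416, exactly the target accrual. Nothing was added for weighting or clustering.

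**3. How much inflation the plan can absorb.** Let DE be the net design effect, the factor by which weighting and clustering together multiply the variance. Power stays at 80% while margin/(SE√DE) ≥ 2.638 + 0.842 = 3.480.

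- B: DE ≤ (3.481/3.480)² ≈ 1.00
- A: DE ≤ (3.541/3.480)² ≈ 1.035

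**4. Power under assumed design effects.** Power = Φ(margin/(SE√DE) − 2.638). The protocol gives no intracluster correlation (ICC), cluster size or weight variability, so every DE here is an assumption.

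| DE | Power B | Power A | WGL patients needed to restore B (1854 × DE) |
|---|---|---|---|
| 1.0 | 80.0% | 81.7% | 1854 |
| 1.1 | 75.2% | 77.0% | 2040 |
| 1.2 | 70.5% | 72.4% | 2225 |
| 1.5 | 58.1% | 60.0% | 2781 |

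Example: 20 patients per site, ICC 0.01 and technique constant within site give DE = 1 + 19 × 0.01 = 1.19 before any loss from weighting, and 71.0% power for B.

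**5. Error if the intervals ignored the design effect.** One-sided error at the margin = 1 − Φ(2.638/√DE): 0.80% at DE 1.2 and 1.56% at DE 1.5, against 0.417%. This applies only if the intervals use a variance that ignores DE.

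**6. Does a clustered sandwich variance repair this?** For A, 927 × 0.6% ≈ 5.6 failures are expected per experimental group. A simulation at the margin (failure 1.7% against 0.6%, 40 patients per site, technique constant within site, no weights) gives these approximate one-sided errors for plain Wald intervals:

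| Endpoint, ICC | Naive variance | Site-clustered sandwich |
|---|---|---|
| A, 0 | 1.3% | 1.6% |
| A, 0.01 | 3% | 2% |
| B, 0.01 | 1.4% | 0.8% |

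Clustering helps for B. For A, the error stays several times the nominal 0.417%, because events are rare.

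**The case against.** A reader might infer that the planned intervals are too narrow and that the family-wise error exceeds 5%. The protocol does not support that as a fact. The t-tests only order the hypotheses, and ordering alone cannot raise the family-wise error: in any order, the first true null is tested at no more than 5% divided by the number of true nulls. Rejection rests on intervals whose variance is not stated and may be set as robust or clustered in an analysis plan not at hand. Nor are the t-tests said to be unweighted: the weights are to enter all primary comparisons, and Step 2 mentions an estimated regression coefficient.

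It is also tempting to read section 4.4 as saying that each site uses one technique. It does not. Section 4.5 lets a site enrol in several cohorts, and section 4.3 allows more than one technique. Comparison within sites would shrink, and could even reverse, the clustering penalty. The re-operation range in section 3 comes from population-based studies; it concerns neither primary endpoint and is not an ICC. Correlation between lesions of one patient matters only if lesions are the unit, and the protocol counts patients.

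These objections stand against any claim of a known error or a known power loss. They do not rescue the power statement, which needs a net design effect of 1.00 for B. The protocol gives no reason to expect that, and the figure is fixed in section 7.1, not deferred.

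**Conclusion.** The point holds as a planning defect that should be corrected. The stated power belongs to an unweighted analysis of independent patients, whereas the planned analysis is weighted and its patients are nested in sites. B has no reserve and A has about 3.5% in variance. For design effects of 1.1 to 1.5, power would be 75% to 58% for B and 77% to 60% for A. That range is an assumption, and the true loss cannot be derived from the protocol. It is smaller where sites use both techniques. Intervals that are too narrow are a conditional risk: they arise if the variance of an ordinary t-test is carried into Steps 3 and 4 and technique varies mostly between sites.

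**What to change.** **Section 7.1.** Replace the single figure of 80.04% with power over a justified range of design effects covering weighting and site clustering, and state the assumed cluster size, ICC and weight variability. Give both endpoints. Enrolment need not change.

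**Section 7.2.** Replace the t-tests with the IPT-weighted risk difference with variance clustered on Site ID, and use that one estimate for both the Holm ordering and the intervals of Steps 3 and 4. For endpoint A, do not use a plain Wald sandwich interval; name a method suited to rare events, such as a site-level cluster bootstrap or a small-sample-corrected or score-type interval.

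**Cost.** Some programming, probably wider intervals and a lower stated power. No new data are needed, because the Site ID is already the prefix of each Patient ID (section 5).
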